#### **10.1.5      *Sponsor Safety Reporting to Regulatory Authorities***

The Sponsor or its representative is required to report certain study events in an expedited manner to the Food and Drug Administration, the European Medicines Agency's EudraVigilance electronic system according to Directive 2001/20/EC, and to all country Regulatory Authorities where the study is being conducted, according to local applicable regulations.

The following describes the safety reporting timeline requirements for SUSARs and other reportable events:

##### **Immediately and within 7 calendar days:**

- Any suspected adverse reaction that is associated with the use of the study drug, unexpected, and fatal or life-threatening. Follow-up information must be reported in the following 8 days.

##### **Immediately and within 15 calendar days:**

- Any suspected adverse reaction that is associated with the use of the study drug, unexpected, and serious, but not fatal or life-threatening, and there is evidence to suggest a causal relationship between the study drug and the reaction.
- Any finding from tests in laboratory animals that suggest a significant risk for human patients, including reports of mutagenicity, teratogenicity, or carcinogenicity.
- Any event in connection with the conduct of the study or the development of the study drug that may affect the safety of the study patients. In addition, periodic safety reporting

to regulatory authorities will be performed by the Sponsor or its representative according to national and local regulations.

## **10.2 Data Management**

Source documents will be maintained by sites and used to enter data and complete the eCRFs in the clinical database (EDC or Clinical Data Management System [CDMS]). The Sponsor's monitors will routinely review the source documentation and verify the corresponding data entered on eCRFs in the clinical database. All entered, changed, and final data shall be available with a validated audit trail report or data extract report. The eCRFs shall be considered complete when all expected data has been entered and all discrepancies have been resolved or documented.

The Investigator must sign all eCRFs according to the EDC (CDMS) requirements.

### **10.2.1 Data Protection**

Participants will be assigned a unique identifier by the sponsor to protect the participant's personal data. Any participant information, such as records, datasets or tissue samples that are transferred to the sponsor will contain the identifier only. Participant names or any information which would make the participant identifiable will not be transferred.

The participant must be informed that the participant's personal study-related data will be used by the sponsor in accordance with local data protection law. The level of disclosure must also be explained to the participant who will be required to give consent for their data to be used as described in the informed consent. This is done by the site personnel through the informed consent process.

The participant must be informed through the informed consent by the site personnel that their medical records may be examined by Clinical Quality Assurance auditors or other authorized personnel appointed by the sponsor, by appropriate IRB/IEC members, and by inspectors from regulatory authorities.

The sponsor has processes in place to ensure information security, data integrity, and data protection. These processes address management of data transfer, and prevention and management of unauthorized access, disclosure, dissemination, alteration or loss of information or personal data. These processes include appropriate contingency plan(s) for appropriate and timely response in the event of a data security breach.

The transfer of personal data is subject to appropriate safeguards through contractual agreements and processes. The sponsor's processes are compliant with local privacy laws and relevant legislations including the General Data Protection Regulation (GDPR).

### **10.3 Study Monitoring**

Prior to the start of the study, the Sponsor's monitor will contact the clinical site to discuss the protocol and data collection procedures and conduct applicable training of site personnel. The Sponsor and its designees will also periodically contact the clinical site during the conduct of the study (which will include on-site visits) in accordance with applicable regulations and Good Clinical Practices (GCP). During these contacts, the monitoring activities will include:

- Checking and assessing the progress of the study.
- Reviewing study data collected to date for completeness and accuracy.
- Conducting source document verifications by reviewing each patient's eCRF against source documents.
- Identifying any issues and addressing resolutions.
- Recording and reporting protocol deviations not previously reported to the Sponsor.
- Confirming that SAEs have been properly reported to the Sponsor and submitted to the IRB/IEC if appropriate.

These activities will be done in order to verify that the data are authentic, accurate, and complete; that the safety and rights of the patient are being protected; and that the study is conducted in accordance with the currently approved protocol, ICH GCP, and all applicable regulatory requirements. Additionally, to ensure compliance with ICH GCP and all applicable regulatory requirements, the Sponsor or designee may conduct a quality assurance audit.

### **10.4 Termination**

Upon completion of the study, the following activities, when applicable, must be conducted by the site monitor and the Investigator:

- Submission of all study data to the Sponsor.
- Completion of all data clarifications and/or resolutions.
- Reconciliation and final disposition of investigational product.
- Review of site study files for completeness.
- In addition, the Sponsor reserves the right to temporarily suspend or prematurely terminate this study for any reason.

If the study is suspended or terminated for safety reasons, the Sponsor will promptly inform the Investigator and will also inform the IRB/IEC with the reasons for the action. In the event of premature termination, all study data must be submitted to the Sponsor. In addition, the clinical site must document final disposition of all unused investigational product in accordance with the Sponsor's procedures.

## **Reports**

The sponsor will disclose a summary of study information, including tabular study results, on publicly available websites where required by local law or regulation.

The summary of results will be posted within the time frame specified by local law or regulation. If the study remains ongoing in some countries and a statistical analysis of an incomplete dataset would result in analyses lacking scientific rigor (for example, underpowered) or compromise the integrity of the overall analyses (for example, trial not yet unblinded), the summary of results will be submitted within 1 year after the end of the study globally or as soon as available, whichever is earlier.

### **10.5 Records Retention**

Patient records, source documents, monitoring visit logs, investigational product inventory, regulatory documents, and other correspondence pertaining to the study must be maintained in the appropriate site study files according to ICH GCP and applicable regulatory requirement(s). These records will be retained for the period required by the institution or site policy. Prior to transfer or destruction of these records, the Sponsor must be notified in writing.

### **10.6 Confidentiality of Information**

Patient names will remain confidential and will not be supplied to the Sponsor or its designee. The Investigator will maintain a personal patient identification list (patient and treatment numbers with the corresponding patient names) to enable records to be identified.

## **11. APPENDICES**

**Appendix A      Examples of Multikinase Inhibitors (MKIs) with Anti-RET Activity**

**Table 11-1      Examples of Multikinase Inhibitors (MKIs) with Anti-RET Activity**

Multikinase Inhibitors
cabozantinib
vandetanib
lenvatinib
alectinib
ponatinib
regorafenib
sunitinib
sorafenib
motesanib
RXDX-105
sitravatinib (MGCD516)

## Appendix B Examples of *RET* Activating Mutations

**Table 11-2 Examples of *RET* Activating Mutations**

Exon	RET mutation
5	V292M, G321R
8	A510V, E511K, C515S, C531R, G533C
10	V591I, R600Q, K603E/Q, Y606C, C609F/G/R/S/W/Y, C611F/G/R/S/W/Y, C618F/G/R/S/W/Y, C620F/G/R/S/W/Y
11	C630R/Y, D631Y, E632K, C634F/G/R/S/W/Y, S649L, K666E/M
13	E768D, R770Q, N777S, V778I, Q781R, L790F
14	V804L, V804M, Y806C, E819K, R833C, R844Q, R866W, M848T
15	L881V, A883F/S/T/V, R886W, S891A, S904C/F
16	G911D, R912P, M918T, E921K, S922P, T930M
Complex	D631del, E632-L633del, D898-E901del, E632-A639> HR
Other	Because the list of published activating RET mutations is constantly being updated, other mutations (e.g., other complex mutations, overlapping deletions, substitutions with different amino acids at the same site) may be eligible if a compelling rationale is provided by the Investigator and approved by the Sponsor.

References: (Dvorakova, Vaclavikova et al. 2008, Agrawal, Jiao et al. 2013, Krampitz and Norton 2014, Ji 2015, Oh et al. 2015, Wells, Asa et al. 2015, Heilmann, Subbiah et al. 2016, Romei, Casella et al. 2016, Kato 2017, Subbiah et al. 2017).

For all other non-MTC cancers with *RET* mutation, the Sponsor should have final determination regarding eligibility based upon review of all genomic findings.

## Appendix C Examples of Validated Oncogenic Drivers

The following are example oncogenic drivers that may cause resistance to selpercatinib.

**Table 11-3 Examples of Validated Oncogenic Drivers**

Tumor Type	Oncogenic Driver(s)
NSCLC	Targetable mutation in EGFR or MET , targetable rearrangement involving ALK or ROS1 , or activating mutation in KRAS
Thyroid (non-MTC)	Targetable mutation in BRAF , NTRK fusion, or activating mutation in RAS genes
MTC	Targetable rearrangement involving ALK , NTRK fusion, or activating mutation in RAS genes
Pancreatic	Activating mutation in KRAS
Colorectal	Targetable mutation in BRAF or PIK3CA or activating mutation in RAS genes
Breast	Targetable mutation in PIK3CA or alteration in HER2
Other	Targetable mutation/rearrangement known to occur in the specific disease type

## Appendix D Inhibitors and Inducers of CYP3A4

**Note:** Non-systemic (e.g., topical creams, eye drops, mouthwashes, etc.) applications of the following are permissible.

**Table 11-4 Inhibitors of CYP3A4**

Strong inhibitors a	Moderate inhibitors b
boceprevir	amprenavir
clarithromycin	aprepitant
conivaptan	atazanavir
grapefruit juice	ciprofloxacin
indinavir	darunavir
itraconazole	diltiazem
ketoconazole	erythromycin
lopinavir	fluconazole
mibefradil	fosamprenavir
nefazodone	imatinib
nelfinavir	verapamil
posaconazole	
ritonavir	
saquinavir	
telaprevir	
telithromycin	
voriconazole	

Abbreviations: AUC = area under the concentration versus time curve; CYP3A4 = cytochrome P450 3A4.

a Increases the AUC of the substrate by  $\geq 5$ -fold.

b Increases the AUC of the substrate by 2- to 5-fold.

**Table 11-5 Inducers of CYP3A4**

Strong inducers a	Moderate inducers b
avasimibe	bosentan
carbamazepine	efavirenz
enzalutamide	etravirine
phenytoin	modafinil
rifampin	nafcillin
St John's wort	

Abbreviations: AUC = area under the concentration versus time curve; CYP3A4 = cytochrome P450 3A4.

a Decreases the AUC of the substrate by  $\geq 80\%$ .

b Decreases the AUC of the substrate by 50–80%.

Note: The above lists are not exhaustive. See also:

<http://www.fda.gov/drugs/developmentapprovalprocess/developmentresources/druginteractionslabeling/ucm093664.htm>.

## Appendix E Proton Pump Inhibitors (PPIs)

Since selpercatinib is more soluble in an acidic environment than a neutral one, absorption may be impacted by stomach acidity. Therefore, the concomitant use of proton pump inhibitors (PPIs) is restricted. If PPIs cannot be avoided, selpercatinib should be taken with food.

**Table 11-6 Examples of Proton Pump Inhibitors (PPIs)**

Omeprazole (Prilosec ® )
Esomeprazole (Nexium ® )
Lansoprazole (Prevacid ® )
Pantoprazole (Protonix ® )
Rabeprazole (Aciphex ® )
Dexlansoprazole (Dexilant ® )

## Appendix F Performance Scales

**Table 11-7 Eastern Cooperative Oncology Group (ECOG) Performance Scale**

Grade	Description
0	Fully active, able to carry on all pre-disease performance without restriction
1	Restricted in physically strenuous activity, but ambulatory and able to carry out work of a light or sedentary nature, e.g., light house work, office work
2	Ambulatory and capable of all self-care, but unable to carry out any work activities. Up and about more than 50% of waking hours
3	Capable of only limited self-care, confined to bed or chair more than 50% of waking hours
4	Completely disabled. Cannot carry on any self-care. Totally confined to bed or chair
5	Dead

**Table 11-8 Lansky Performance Status (< 16 years old)**

Score	Lansky Description
100%	Fully active, normal
90%	Minor restrictions in strenuous physical activity
80%	Active, but tired more quickly
70%	Greater restriction of play and less time spent in play activity
60%	Up and around, but active play minimal; keeps busy by being involved in quieter activities
50%	Lying around much of the day, but gets dressed; no active playing, participates in all quiet play and activities
40%	Mainly in bed; participates in quiet activities
30%	Bed bound; needing assistance even for quiet play
20%	Sleeping often; play entirely limited to very passive activities
10%	Doesn't play; doesn't get out of bed
0%	Unresponsive

Source: (Lansky, S. B., List M. A. et al. 1987).

## **Appendix G      Tumor Measurements and Assessment of Disease Response using RECIST, Version 1.1**

Tumor measurements are to be performed for all patients during Screening as follows (as summarized in Section 7.1):

- Baseline disease assessment: radiographic tumor measurements using CT) or magnetic resonance imaging (MRI) of chest, abdomen, and pelvis, and any other areas with suspected disease involvement, and CT or MRI of brain within 28 days of C1D1. For brain imaging, MRI without and with contrast is preferred, CT without and with contrast is acceptable if MRI is medically contraindicated. For each modality, IV and oral contrast should be utilized (chest CT does not require IV contrast) where applicable unless medically contraindicated. If CT/PET is utilized, the CT component of CT/PET must be of the same quality as a dedicated diagnostic CT scan, i.e., with IV and oral contrast, and 5 mm or less slice thickness.

### **Notes:**

- In patients with thyroid and other head and neck cancers, imaging of the relevant areas (e.g., neck, skull base) is required at baseline; other areas of scanning may differ depending on disease type. See Imaging Manual for details.
- Additional scans can be performed as needed to evaluate potential sites of disease.
- Disease assessments will utilize RECIST 1.1 or RANO, as appropriate to tumor type (refer to Section 7.8.1).
- Guidelines on the technical parameters of how scans should be performed will be provided in a separate Imaging Manual that will be distributed to the sites.

Thereafter, tumor measurements and disease response assessments are to be performed as follows (as summarized in Section 7.3):

- Radiographic disease assessment: every 8 weeks ( $\pm 7$  days) beginning with C3D1 through C13D1 and every 12 weeks ( $\pm 7$  days) thereafter until PD, withdrawal of consent, or initiation of a new anticancer therapy(ies), including imaging, of the chest, abdomen, and pelvis, utilizing the same modality(ies) as used for the baseline imaging assessment. Additionally, any studies performed at baseline that are positive for sites of disease should be repeated at all post baseline assessments. Additional studies can also be performed as clinically indicated. Please see the Site Imaging Manual for guidelines on how the various imaging studies should be performed.

### **Notes:**

Patients who have an ongoing CR or PR and discontinue study drug for reasons other than PD (e.g., AE, noncompliance, etc.) may (but, for practical reasons and to minimize patient inconvenience, are not required to) have scans collected as defined above.

Post-baseline imaging of the brain using the same modality as at baseline should be performed for patients with evidence of CNS disease at baseline, and if clinically indicated.

If consistent with local regulatory guidelines, an initial post-baseline assessment after 4 weeks of treatment ( $\pm 7$  days) is encouraged. If this scan is performed, the next scan should continue according to the schedule above (beginning at C3D1).

- If consistent with local regulatory guidelines, confirmatory imaging a minimum of 4 weeks (e.g., 28 days) after the first imaging studies that demonstrate a tumor CR or PR by RECIST 1.1 or RANO, as appropriate to tumor type, is encouraged. If this scan is performed, the next scan should continue according to the schedule above.

Such assessments also are to be performed at the EOT visit if they had not been performed within the previous 2 cycles.

Anatomical measurements (summed across target lesions) will be documented during Screening and each subsequent evaluation. When possible, the same qualified physician will interpret results to reduce variability. Radiographic images will be maintained at the study site and sent to a central image collection warehouse. Central reading of some or all of the scans may be performed by a third-party vendor who has expertise in evaluating image data. Test results and Investigator's findings will be filed in the patient's source documents.

During Screening, tumor lesions are to be categorized as measurable versus non-measurable and target versus non-target, as follows.

#### ***Measurable versus non-measurable***

- Measurable: Lesions that could accurately be measured in at least one dimension, the longest diameter in the plane of measurement to be recorded as:
  - Tumor lesions:  $\geq 10$  mm by CT scan

Malignant lymph nodes: To be considered pathologically enlarged and measurable, the node must be  $\geq 15$  mm in short axis when assessed by CT scan. At baseline and in follow up, only the short axis will be measured and followed. Nodes that have a short axis  $< 10$  mm are considered non-pathological and should not be recorded or followed.
- Non-measurable: All other lesions, including small lesions (longest diameter  $< 10$  mm or pathological lymph nodes with  $\geq 10$  to  $< 15$  mm short axis), and truly non-measurable lesions.

#### ***Target versus non-target***

- Target: All measurable lesions up to a maximum of 2 lesions per organ and 5 lesions in total, representative of all involved organs, are to be identified as target lesions and measured and recorded at Screening. Target lesions are to be selected on the basis of their size (i.e., those with the longest diameter) and suitability for accurate repeated measurement. Lymph nodes may be selected as target lesions; they must be defined as measurable, and only the short axis of the node will contribute to the baseline sum. All

other pathologic nodes with short axis  $\geq 10$  mm but  $< 15$  mm should be considered non-target lesions.

- Non-target: All other lesions not classified as target lesions (or sites of disease) are to be identified as non-target lesions and are to be recorded in the eCRF. Measurement of non-target lesions is not required.

The sum of the diameters (longest for non-nodal lesions and short axis for nodal lesions) for all target lesions is to be calculated and recorded in the eCRF as the baseline sum diameters.

Disease response in target and non-target lesions will be assessed by the Investigator using RECIST 1.1, according to the categories and criteria described in [Table 11-9](#). The best overall response for each patient will be reported as the best response documented over the sequence of objective statuses recorded using the categories and criteria in [Table 11-10](#).

**Table 11-9 Response Evaluation Criteria in Solid Tumors (RECIST Version 1.1)  
Guidelines for Tumor Response**

Disease Response Criteria for Target and Non-Target Lesions	
Evaluation of Target lesions	
Complete Response (CR):	Disappearance of all target lesions. Any pathologic nodes (whether target or non-target lesions) must have a reduction in short axis diameter (SAD) to less than 10 mm.
Partial Response (PR):	At least a 30% decrease in the sum of the diameters (SOD) (LD for non-nodal lesions and SAD for nodal lesions) of target lesions, taking as reference the baseline sum LD.
Stable Disease (SD):	Neither sufficient shrinkage to qualify for PR nor sufficient increase to qualify for PD, taking as reference the smallest sum LD since the treatment started.
Progressive Disease (PD):	At least a 20% increase in the sum of the diameters of target lesions, taking as reference the smallest sum on study (this includes the baseline sum if that is the smallest sum on study). In addition to the relative increase of 20%, the sum must also demonstrate an absolute increase of at least 5.0 mm. (Note: the appearance of one or more new lesions is also considered progression).
Evaluation of Non-Target Lesions	
Complete Response (CR):	Disappearance of all non-target lesions and normalization of tumor marker level.
Incomplete Response/ Stable Disease (SD):	Persistence of one or more non-target lesion(s) or/and maintenance of tumor marker level above the normal limits.
Progressive Disease (PD):	Appearance of one or more new lesions and/or unequivocal progression of existing non-target lesions.

Abbreviations: LD = longest diameter.

Source: (Eisenhauer, Therasse et al. 2009). Available at:

[https://ctep.cancer.gov/protocolDevelopment/docs/recist\\_guideline.pdf](https://ctep.cancer.gov/protocolDevelopment/docs/recist_guideline.pdf).

**Table 11-10 Overall Response Criteria: Time Point Response**

Patients with Target and Non-Target Lesions			
Target Lesions	Non-Target Lesions	New Lesions	Overall Response
CR	CR	No	CR
CR	Non-CR / Non-PD	No	PR
CR	Not evaluated	No	PR
PR	Non-PD or not all evaluated	No	PR
SD	Non-PD or not all evaluated	No	SD
Not evaluated	Non-PD	No	NE
PD	Any	Yes or no	PD
Any	PD	Yes or no	PD
Any	Any	Yes	PD
Patients with Non-Target Lesions Only			
Non-Target Lesions	New Lesions		Overall Response
CR	No		CR
Non-CR / Non-PD	No		Non-CR / Non-PD
Not all evaluated	No		NE
Unequivocal PD	Yes or No		PD
Any	Yes		PD

Abbreviations: CR = complete response; NE = inevaluable; PD = progressive disease; PR = partial response; SD = stable disease.

Source: (Eisenhauer, Therasse et al. 2009). Available at:  
<http://www.eortc.be/recist/documents/RECISTGuidelines.pdf>

## Appendix H Response Assessment in Neuro-Oncology (RANO) Criteria for Primary CNS Malignancies

The RANO criteria ([Ellingson, Wen et al. 2017](#)) were developed to evaluate efficacy of investigational agents in glioblastoma clinical trials, and have been more broadly utilized for lower grade primary CNS malignancies. These criteria were developed in part to address issues faced when assessing some lesions based on MacDonald criteria, particularly lesions with central necrosis and with a T2 component.

**Table 11-11 Response Assessment in Neuro-Oncology (RANO) Criteria**

RESPONSE CATEGORY	CRITERIA
Complete Response	Disappearance of all measurable and non-measurable enhancing disease Stable or improved non-enhancing FLAIR/T2 lesions No new lesions Clinically stable or improved with no reliance on corticosteroids (except for physiological replacement)
Partial Response	$\geq 50\%$ decrease from baseline of all measurable enhancing lesions No progression of non-measurable disease Stable or improved non-enhancing FLAIR/T2 lesions No new lesions Clinically stable or improved, with stable or reduced corticosteroids compared to baseline
Progressive Disease	$\geq 25\%$ increase from baseline in enhancing lesions despite stable or increasing steroid dose Significant increase in non-enhancing FLAIR/T2 lesions not attributable to other non-tumor causes Any new lesions Clinical deterioration not attributable to other non-tumor causes and not due to steroid decrease
Stable Disease	Does not meet other criteria for response or progression Stable non-enhancing FLAIR/T2 lesions Clinically stable with stable or reduced corticosteroids compared to baseline

Abbreviations: FLAIR/T2 = T2-weighted fluid-attenuated inversion recovery; RANO = Response Assessment in Neuro-Oncology.

A measurable lesion is evaluated by contrast-enhancing MRI and:

- Has clearly defined margins
- Is visible on two or more axial slices, preferably  $< 5$  mm thick
- At least 10 mm in size if slice thickness is  $< 5$  mm (or  $2 \times$  slice thickness if  $> 5$  mm)
- Does not measure a cystic cavity

Non-measurable lesions are those that do not fit the criteria above, and specifically lesions that are cystic, necrotic, or include a surgical cavity should not be considered measurable.

Measurements are calculated by summing the products of perpendicular diameters of all measurable enhancing lesions.

If there are multiple contrast-enhancing lesions, a minimum of the two largest lesions should be measured. However, emphasis should be placed on selecting lesions that allow reproducible repeated measurements. For patients who have multiple lesions for which only one or two are increasing in size, the enlarging lesions should be considered the target lesions for evaluation of response.

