### **8.5.3      *Efficacy Analyses***

The efficacy analyses will be conducted on the Safety Analysis Set of patients with at least 6 months of treatment from the first dose of selpercatinib. These analyses will be summarized per tumor indication, including patients from both the Phase 1 and Phase 2 portions. A Statistical Analysis Plan (SAP) will provide specific details on the efficacy analysis set.

ORR will be assessed using RECIST 1.1 ([Table 11-9](#)) or RANO ([Table 11-11](#), for patients with primary CNS tumors), as appropriate to tumor type. The estimate of the ORR will be calculated based on the maximum likelihood estimator (i.e., crude proportion of patients with best overall response of CR or PR that are confirmed based on RECIST 1.1 or RANO). The estimate of the ORR will be accompanied by 2-sided CIs with various coverage probabilities (e.g., 80%, 95%). The analysis of ORR will be conducted both by the responses determined by each Investigator and responses as determined by IRC.

Waterfall plots will be used to depict graphically the maximum decrease from baseline in the sum of longest diameters of target lesions.

DOR will be calculated for patients who achieve CR or PR. For such patients, DOR is defined as the number of months from the start date of CR or PR (whichever response status is observed first) and subsequently confirmed, to the first date that PD is objectively documented. If a patient dies, irrespective of cause, without documentation of PD beforehand, then the patient's date of death will be used to denote the response end date.

PFS will be derived for each patient as the number of months from the date of the first dose of study drug to the earlier of documented PD or death due to any cause. Patients who are alive and without documented PD as of a data analysis cutoff date will be right-censored according to the censoring methods described later in this section. Whenever appropriate, the same censoring methods will be used for DOR.

OS will be derived for each patient as the number of months from the date of the first dose of study drug to the date of death, irrespective of cause. Patients who are alive or lost to follow-up as of a data analysis cutoff date will be right-censored. The censoring date will be determined from the last date the patient was known to be alive or data analysis cutoff date, whichever occurs first.

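### RANO size progression is measured from baseline, so a responding primary CNS tumour must regrow at least 2.5-fold in summed area before size alone counts as progression

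*Protocol*

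**What the plan says.** Appendix H of the protocol gives the RANO criteria for primary CNS malignancies. In Table 11-11, partial response requires at least a 50% "decrease from baseline of all measurable enhancing lesions". Size-based progression requires at least a 25% "increase from baseline in enhancing lesions despite stable or increasing steroid dose". Both thresholds use baseline. Neither the table nor the notes below it mention a nadir or a smallest on-study value. The metric is an area: "Measurements are calculated by summing the products of perpendicular diameters of all measurable enhancing lesions".

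Table 11-11 also lists progression routes without the 25% threshold: any new lesion, "Significant increase in non-enhancing FLAIR/T2 lesions not attributable to other non-tumor causes", and "Clinical deterioration not attributable to other non-tumor causes and not due to steroid decrease". A note covers patients in whom only one or two of several lesions grow: "the enlarging lesions should be considered the target lesions for evaluation of response".

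The RECIST 1.1 criteria in Table 11-9 (Appendix G) use a different reference for progression: "taking as reference the smallest sum on study (this includes the baseline sum if that is the smallest sum on study".

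Protocol Section 8.5.3 assigns Table 11-11 "for patients with primary CNS tumors), as appropriate to tumor type". The same section ends DOR and PFS at the first documented progression or at death. The SAP defines ORR by RECIST 1.1 only (Sections 1.1, 4.3 and 4.3.1) and does not mention RANO.

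**The concern.** One protocol uses two reference points for progression and gives no reason for the difference. Under Table 11-9, a tumour that has shrunk and is growing again is compared with its own best result. Under Table 11-11, it is compared with its size before treatment, so all the shrinkage has to be undone before the 25% starts to count. The better the response, the less sensitive the rule is to regrowth.

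DOR and PFS both end at documented progression, so a later progression date lengthens both. The smallest on-study value cannot exceed baseline, so a baseline reference can never date size-based progression earlier than a nadir reference would. Any error therefore goes one way. DOR is the more exposed endpoint, because by definition it includes only patients whose tumours shrank.

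Progression as defined by the protocol is also a listed reason for removal from treatment (Section 6.4) and a condition attached to starting new systemic therapy (Section 6.3.3). The response definition thus reaches beyond the analysis.

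**Working it through.** The plan states no figure for this rule, so there is nothing to reproduce. The check is arithmetic on the stated thresholds.

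**Inputs from the protocol**
- Partial response: at least a 50% decrease from baseline, so smallest sum ≤ 0.50 × baseline (Table 11-11).
- Size-based progression: sum ≥ 1.25 × baseline (Table 11-11).
- Metric: summed products of perpendicular diameters (Appendix H).
- Scans: every 8 weeks through C13D1, then every 12 weeks (Section 7.3).

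**Step 1. Regrowth needed.** Let *d* be the best proportional decrease, so the smallest sum is (1 − *d*) × baseline.
- As written: fold regrowth from the smallest sum = 1.25 / (1 − *d*).
- With the smallest sum as reference: 1.25 for every *d*. The threshold is then 1.25 × (1 − *d*) of baseline.

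| Best decrease | Fold regrowth, as written | Threshold as share of baseline, smallest-sum reference | Extra area doublings, log2[1/(1 − *d*)] |
|---|---|---|---|
| 0% | 1.25 | 1.250 | 0 |
| 50% | 1.25/0.50 = 2.50 | 0.625 | 1.00 |
| 60% | 1.25/0.40 = 3.125 | 0.500 | 1.32 |
| 75% | 1.25/0.25 = 5.00 | 0.3125 | 2.00 |
| 90% | 1.25/0.10 = 12.5 | 0.125 | 3.32 |

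These folds are in area. With uniform growth, 2.5-fold in area is √2.5 = 1.58-fold in diameter.

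*Example.* A summed area falls to 40% of baseline and regrows to 120%. It has tripled (1.20/0.40 = 3), yet 120% is below the 125% threshold. Against the smallest sum, the threshold would have been crossed at 50% of baseline.

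**Step 2. Extra time.** Assume exponential regrowth from the smallest value, with area-doubling time *T*. The time to threshold is *T* × log2(1.25) with the smallest-sum reference and *T* × log2[1.25/(1 − *d*)] as written. The difference is *T* × log2[1/(1 − *d*)], which is one doubling time at 50% and two at 75%.

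**Step 3. On the scan grid.** The documents give no doubling time, so *T* is taken over 4 to 24 weeks. The smallest value is assumed to fall at a scan, and each crossing is dated to the next 8-weekly scan.

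| *T* (weeks) | Smallest-sum reference: crossing → scan | As written, 50% decrease: crossing → scan | Delay | As written, 75% decrease: crossing → scan | Delay |
|---|---|---|---|---|---|
| 4 | 1.3 → 8 | 5.3 → 8 | 0 | 9.3 → 16 | 8 |
| 8 | 2.6 → 8 | 10.6 → 16 | 8 | 18.6 → 24 | 16 |
| 16 | 5.2 → 8 | 21.2 → 24 | 16 | 37.2 → 40 | 32 |
| 24 | 7.7 → 8 | 31.7 → 32 | 24 | 55.7 → 56 | 48 |

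After C13D1 the grid is 12-weekly, so delays there would move in 12-week steps.

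**The case against.** The strongest reply is that no planned estimate is shown to move. The SAP covers the final study report and uses RECIST 1.1 throughout. None of its efficacy sets is a primary CNS tumour set, and RET fusion-positive cancers other than NSCLC and thyroid are left to another report (SAP Section 2.1). The number of RANO-assessed patients is not stated and could be zero. This stands: a reader might infer that the trial's headline DOR and PFS are overstated, and the documents do not support that.

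A reader might also carry the point over to brain metastases, since the protocol objectives mention RECIST 1.1 or RANO for CNS response. Appendix H is confined to primary CNS malignancies. The SAP defines its CNS response set by RECIST lesions in NSCLC (Section 2.2) and reads CNS response under the IRC charter (Section 4.3.4), so that extension is not supported either.

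Other progression routes may come first. The tripled tumour in the example counts as stable only with no new lesions, stable FLAIR/T2 findings and a stable clinical state. The note on enlarging lesions matters too: if a subset becomes the target, the fold is 1.25 divided by that subset's own smallest-to-baseline ratio, which can be below 2.5. The note changes the lesions followed, not the reference point.

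Finally, RECIST and RANO are separate systems with different metrics and thresholds, so a difference between them is not an error in itself. Whether the published RANO source requires a nadir reference cannot be checked from the documents, and the point does not rely on it. What remains is an unexplained difference inside one protocol, with a one-sided effect on endpoints that both tables feed. The IRC charter is not available, so one cannot conclude that IRC dates are wrong. Investigators are nonetheless directed to Appendix H (Section 7.8.1), although that section also refers to the Imaging Manual and allows a comparable method.

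**Conclusion.** The point holds, with narrow reach. As written, Table 11-11 requires at least 2.5-fold regrowth of the summed enhancing area after a partial response, and 5-fold after a 75% decrease, where a smallest-sum reference would require 1.25-fold. Protocol-defined DOR and PFS in RANO-assessed patients can only be biased upward by this. The bias arises only where enhancing size would be the first trigger. Every RANO partial responder faces the higher threshold on the whole sum, but not every progression date shifts. Patients whose tumours never shrink below baseline are unaffected. After a complete response the fold is undefined, and reappearing disease may count as a new lesion.

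The fold figures follow from the protocol alone. The delays, 0 to 24 weeks at 50% shrinkage and 8 to 48 weeks at 75%, rest on the assumed doubling times, exponential regrowth, a smallest value that falls at a scan, and the 8-weekly grid. The effect on any reported estimate cannot be sized without the number of RANO-assessed patients. The SAP's NSCLC, MTC and thyroid results should be unaffected.

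**What to change.** - In Table 11-11, reference the 25% increase to the smallest on-study sum of products (baseline if that is the smallest), and reconcile it with Table 11-9.
- Check the IRC charter and align it, so that investigator and IRC progression dates rest on the same rule.
- Where RANO-assessed patients enter a reported DOR or PFS analysis, re-derive size-based progression dates from stored measurements, but only for assessments that used the baseline reference. If the IRC already used the smallest value, its dates need no change.
- Leave to the sponsor how the reconciled definition bears on treatment decisions in Sections 6.3.3 and 6.4. Those passages must agree with the response criteria, and no treatment rule is proposed here.

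The cost is one table cell, a check of the charter and, if needed, a re-derivation from data already collected. Section 7.8.2 provides for all scans to be stored centrally. No new assessments are required.
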